7.4. Data sources

The data will be recorded using an electronic case report form (eCRF) for each patient included. The completed eCRFs are the sole property of Pfizer and must not be provided to third parties in any format without the written approval of Pfizer, with the exception of authorized representatives of Pfizer or the appropriate competent authorities.

The treating physician is ultimately responsible for the collection and reporting of all clinical data, safety and laboratory data entered on the eCRFs and other forms for data collection (source documents) and must guarantee that they are accurate, authentic/original, traceable, complete, consistent, legible, timely (contemporaneous), permanent, and available as required. The eCRFs must be signed by the treating physician or authorized personnel.

All corrections of entries on the eCRFs must be explained (reason for change) and signed off (electronic signatures) if available signature was broken. Corrections of entries are automatically recorded by the system (incl. date of change, user changing data, old and new value, reason for change).

In most cases, the source documents are patient records in the hospital or at the doctor's office. In these cases, the data collected on the eCRFs must match the data in these records.

In some cases, the eCRF or part of the eCRF can also serve as a source document. In these cases, a document must be available at the doctor's study site and at Pfizer and must clearly identify the data recorded in the eCRF and for which the eCRF is considered a source document.

The clinical parameters recorded, especially those used to assess efficacy, are usual, known and recognized variables within each respective indication.

7.5. Study procedure

Patients attending can be included by the HCP if they fulfil all selection criteria for the study and are started on treatment with Tofacitinib for moderate to severely active rheumatoid arthritis.

All visits shall be scheduled according to clinical practice. The treatment of a patient is independent from the patient enrolment into the study. Within this study 9 visits may be documented. At each visit patients will undergo procedures in compliance with the country label and as per standard of care. In order to collect comparable study data, visits 2 to 9 occurring +/- 14 days of the scheduled visit date will be used for data analysis.

After a training session the sites will get access to the eCRF, where the data and findings of the patient are documented. Additionally a folder with questionnaires will be provided. The collection of all data is prospective.

Dose and duration of treatment should be based on clinical and individual needs and are determined by the treating physician. To provide accurate information regarding the treatment, the initial Tofacitinib dose and all changes and the reasons for changes are documented during the course of the evaluation. The concomitant treatment of rheumatoid arthritis with Glucocorticoids is determined by the treating physician and is registered in the documentation sheet.

7.5.1. Study Period

The planned observation period of each patient is 24 months. In this time period, up to 9 visits will be documented.

7.5.1.1. Baseline visit

The following parameters will be documented at baseline visit

- Informed Consent.
- Prognostic factors (from prior history)
- Documentation of initial diagnosis of RA
- Documentation of relevant comorbidities
- Demographic data
- Documentation of insurance type
- Physical Examination (weight, height)
- Smoking history and current smoking status
- Inclusion/ Exclusion criteria according to protocol
- Varicella vaccination status
- RA-Treatment with Tofacitinib and/or other DMARDs
- Prior drug treatment of RA
- Concomitant treatment of RA with Glucocorticoids
- Inflammatory Markers:
 - Erythrocyte sedimentation rate (ESR)

- C-reactive protein (CRP)
- Number of swollen and tender joints
- Duration of Morning stiffness
- Patient's Global Assessment of Arthritis
- Physician's Global Assessment of Arthritis
- Patient's Assessment of Arthritis Pain
- Functional Ability Questionnaire Hannover (FFbH)
- EuroQoL EQ-5D-3L Health State Profile
- FACIT – Fatigue Scale
- Patient's overall satisfaction with prior drug treatment

7.5.1.2. Scheduled Visits 2- 8 /month 3 – month 21

Following parameters will be documented at each interim visit:

- RA treatment with Tofacitinib and/or other DMARDs
- Concomitant treatment of RA with Glucocorticoids
- Inflammatory Markers:
 - Erythrocyte sedimentation rate (ESR)
 - C-reactive protein (CRP)
- Documentation of Adverse Events (AE)
- Number of swollen and tender joints
- Duration of Morning stiffness
- Patient's Global Assessment of Arthritis
- Physician's Global Assessment of Arthritis

- Patient's Assessment of Arthritis Pain
- Functional Ability Questionnaire Hannover (FFbH)
- EuroQoL EQ-5D-3L Health State Profile
- FACIT – Fatigue Scale
- Patient's satisfaction with drug treatment

7.5.1.3. Final (or close out) Visit 9 / month 24

Following parameters will be documented at final visit:

- RA treatment with Tofacitinib and/or other DMARDs
- Concomitant treatment of RA with Glucocorticoids
- Inflammatory Markers:
 - Erythrocyte sedimentation rate (ESR)
 - C-reactive protein (CRP)
- Documentation of AE
- Number of swollen and tender joints
- Duration of Morning stiffness
- Patient's Global Assessment of Arthritis
- Physician's Global Assessment of Arthritis
- Patient's Assessment of Arthritis Pain
- Functional Ability Questionnaire Hannover (FFbH)
- EuroQoL EQ-5D-3L Health State Profile
- FACIT – Fatigue Scale
- Patient's satisfaction with drug treatment

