6.1. Endpoints

6.1.1. Primary Endpoint:

Impact of the following factors on the number of treatment escalations of Tofacitinib patients in 24 months

- a. DAS28-4 with Erythrocyte Sedimentation Rate (ESR)
- b. Δ DAS28-4 (ESR)
- c. Physician Global Assessment of Arthritis
- d. Patient's Assessment of Arthritis Pain
- e. Patient's satisfaction with drug treatment
- f. Patient's Global Assessment of Arthritis

Treatment escalation in this study is defined as a switch to another DMARD or combination of DMARDs when compared to the last visit.

6.1.2. Secondary Endpoints:

- a) Time to first treatment escalation
- b) Rate of Low Disease Activity (LDA) over time of patients on Tofacitinib (in combination therapy or monotherapy), as assessed by: Simplified Disease Activity Index (SDAI) \leq 11; Clinical Disease Activity Index (CDAI) \leq 10; DAS 28-4 (ESR) \leq 3.2 and DAS28-4 with C-reactive Protein (CRP) \leq 3.2.
- c) Rate of remission over time of patients on Tofacitinib (in combination therapy or monotherapy), as assessed by: American College of Rheumatology (ACR)-EULAR Boolean remission criteria; SDAI \leq 3.3; CDAI \leq 2.8; DAS 28-4 (ESR) $<$ 2.6 and DAS28-4 (CRP) $<$ 2.6
- d) Change from baseline over time of patients on Tofacitinib (in combination therapy or monotherapy) in DAS 28-4 (ESR) and DAS 28-4 (CRP)
- e) Change from baseline of duration of morning stiffness over time of patients on Tofacitinib (in combination therapy or monotherapy)

- f) Change from baseline in the Functional Ability Questionnaire Hannover (FFbH) over time of patients on Tofacitinib (in combination therapy or monotherapy)
- g) Rate of patients with functional remission in FFbH (FFbH > 83%) over time of patients on Tofacitinib (in combination therapy or monotherapy)
- h) Change from baseline in a self-report questionnaire (a quality of life instrument) developed by the European Quality of Life (EuroQoL) Group (EuroQoL EQ-5D) over time of patients on Tofacitinib (in combination therapy or monotherapy)
- i) Change from baseline in Functional Assessment of Chronic Illness Therapy (FACIT)-Fatigue scale over time of patients on Tofacitinib (in combination therapy or monotherapy)
- j) Drug survival at month 12, 24 of patients on Tofacitinib (in combination therapy or monotherapy)
- k) Patient's satisfaction with Tofacitinib treatment (in combination therapy or monotherapy) over time

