Rheumatoid Factor (RF), Anti-citrullinated protein antibodies (ACPA)	Baseline characteristic, potential confounder, sub-group identifier	Case records/eCRF	Details will be provided in Statistical Analysis Plan
Prognosis factors	Baseline characteristic, potential confounder, sub-group identifier	Case records/eCRF	Details will be provided in Statistical Analysis Plan
Prior drug treatment for RA	Potential confounder, sub-group identifier	Case records/eCRF	Details will be provided in Statistical Analysis Plan
Concomitant treatment of RA with Glucocorticoids	Potential confounder, sub-group identifier	Case records/eCRF	Details will be provided in Statistical Analysis Plan
Patient's Global Assessment of Arthritis	Baseline and outcome variable	Case records/eCRF	Details will be provided in Statistical Analysis Plan
Physician's Global Assessment of Arthritis	Baseline and outcome variable	Case records/eCRF	Details will be provided in Statistical Analysis Plan
Patient's Assessment of Arthritis Pain	Baseline and Outcome	Case records/eCRF	Details will be provided in Statistical Analysis Plan
Tender and swollen (28) joint count	Baseline and Outcome	Case records/eCRF	Details will be provided in Statistical Analysis Plan
Duration of Morning Stiffness	Baseline and Outcome	Case records/eCRF	Details will be provided in Statistical Analysis Plan
Functional Ability Questionnaire Hannover (FFbH)	Baseline and Outcome	Case records/eCRF	Details will be provided in Statistical Analysis Plan
EuroQoL EQ-5D-3L Health State Profile	Baseline and Outcome	Case records/eCRF	Details will be provided in Statistical Analysis Plan
Functional Assessment of Chronic Illness Therapy (FACIT) Fatigue Scale	Baseline and Outcome	Case records/eCRF	Details will be provided in Statistical Analysis Plan
Patient's satisfaction with drug treatment	Baseline and Outcome	Case records/eCRF	Details will be provided in Statistical Analysis Plan

Table 6 Variables

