7.6.16. Patient’s satisfaction with drug treatment

Satisfaction with treatment will be assessed on a 5-point Likert scale (where 0 = extremely dissatisfied, 1= dissatisfied, 2 = neither satisfied nor dissatisfied, 3 = satisfied

and 4 = extremely satisfied) in response to the question “How satisfied are you with the drugs that you have received for your arthritis since your last visit?”

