7.9.2.2.3. Change from Baseline

The summary statistics of the absolute value and the change from baseline at each visit will be reported. Change from baseline will be presented for DAS28-4 (ESR) and DAS28-4 (CRP) as well as the scores resulting from the PRO questionnaires; FFbH, EQ-5D-3L, FACIT-Fatigue and Patients satisfaction with treatment.

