8 HANDLING OF MISSING VALUES

8.1 TIME TO EVENT (PRIMARY ANALYSIS, TIME TO FIRST TREATMENT ESCALATION AND DRUG SURVIVAL)

Time to event should be determined for the events without any date imputation.

If a patient experiences the event of interest the status will be 1, and the time will be the time at which the event occurred (or visit at which it was recorded).

If a patient doesn't experience the event of interest the status will be 0, and the time will be the last time that the patient was known to be in the study (last visit). If this is not the end of the study then the time will be censored at this time point.

The primary endpoint is a time-to-event endpoint, although it takes into account the possibility of multiple events occurring for each patient. For each patient the data for analysis should consist of the times at which they experienced the event of interest and the values of the covariates at each time point. Any missing data within the covariates to be included in the models for primary analysis will be replaced by the nearest available value to the event. If more than one value qualifies, the later value will be used .

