9.1.5 ANALYSIS OF CATEGORICAL DATA

Categorical data will be summarized in terms of number and percentage of patients within each category at each visit. Shift tables of changes from baseline will also be presented.

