9.2.3.11 PATIENT'S SATISFACTION WITH DRUG TREATMENT

The Patient satisfaction is measured through a 5-point likert question asked at each visit and will be presented as in Section 9.1.5, using the FAS. At each visit, Visit X, only those who remained on tofacitinib at the previous visit, Visit X-1, will be presented. At each visit the satisfaction will be summarised split by those who remain on tofacitinib at Visit X and those who stop taking tofacitinib at Visit X.

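### Visit 1 satisfaction rates the patient's prior drugs, yet the plan uses it as the baseline for tofacitinib satisfaction and lets it stand in for on-treatment satisfaction at early escalations

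*Protocol*

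**What the plan says.** **Measurement.** The Visit 1 list (Protocol 7.5.1.1) has "overall satisfaction with prior drug treatment". The lists for Visits 2 to 9 have satisfaction with drug treatment. The item is a 0 to 4 scale answering "How satisfied are you with the drugs that you have received for your arthritis since your last visit" (Protocol 7.6.16). Earlier use of tofacitinib or another JAK inhibitor is an exclusion (Protocol 7.2.2), so the Visit 1 answer concerns other drugs.

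**One variable.** Protocol Table 6 gives satisfaction a single entry with the role "Baseline and outcome". Protocol Table 7 gives it one row across all nine visits. SAP 9.2.1 names Visit 1 as the baseline visit.

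**Secondary analysis.** Endpoint (k) in Protocol 6.1.2 is "satisfaction with Tofacitinib treatment (in combination therapy or monotherapy) over time". Protocol 7.9.2.2.3 lists, among the scores analysed as change from baseline, "FFbH, EQ-5D-3L, FACIT-Fatigue and Patients satisfaction with treatment". SAP 9.2.3.11 sends satisfaction to SAP 9.1.5, which states "Shift tables of changes from baseline will also be presented". SAP 9.2.3.11 also says that at each visit "only those who remained on tofacitinib at the previous visit, Visit X-1, will be presented".

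**Primary analysis.** Satisfaction is factor (f) of six in SAP 7.3.1. Under SAP 8.1 a missing covariate "will be replaced by the nearest available value to the event", with ties going to the later value. SAP 9.2.6 marks the primary FAS model as using imputation. SAP 9.2.2 counts escalations assigned to baseline under Month 3. It adds a sensitivity analysis, in the FAS and the per-protocol set (PPAS), that assigns each switch to the visit before it.

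**The concern.** DAS28 and the visual analogue scores mean the same thing at Visit 1 as later, so borrowing them from baseline gives a stale value of the right quantity. Satisfaction differs: between Visit 1 and Month 3 the drug being rated changes. A Visit 1 value used at an early escalation describes the drug the patient had before tofacitinib, while the decision being modelled is whether to leave or modify tofacitinib.

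This bears on a factor that Protocol section 5 singles out for interest. Tofacitinib is indicated after inadequate response or intolerance to a DMARD, so low prior-drug ratings are plausible, although the documents do not report them. If such ratings were attached to escalations more often than to other intervals, dissatisfaction could appear to drive escalation. In the secondary analysis, an unlabelled shift from Visit 1 would present a change of drug as a change in satisfaction with tofacitinib.

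**Working it through.** No sample-size or power figure is involved; satisfaction is not among the five factors in the Protocol 7.7 simulation. The check applies the SAP rules day by day.

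**Inputs (SAP 12.1.1).** Target days are 1, 91, 182 and 273 for Visit 1, Month 3, Month 6 and Month 9. The windows reproduce as tabulated: 91 ± 14 = 77 to 105 and 182 ± 28 = 154 to 210.

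**Step 1: days belonging to Month 3.** The midpoint of Months 3 and 6 is (91 + 182)/2 = 136.5. Escalations nearest Visit 1 are moved to Month 3. Month 3 therefore collects Days 2 to 136, which is 135 days.

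**Step 2: days that borrow Visit 1 when Month 3 satisfaction is missing.** Visit 1 is nearer than Month 6 (on day m) when t − 1 < m − t, that is t < (m + 1)/2.

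| Month 6 rating on day | Last borrowing day | Days borrowing | Share of 135 |
|---|---|---|---|
| 154 (window start) | 77 | 76 | 56% |
| 182 (target) | 91 | 90 | 67% |
| 210 (window end) | 105 | 104 | 77% |
| Month 6 also missing, Month 9 on day 273 | 136 | 135 | 100% |

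If Visit 1 fell on Day −13 or −27 (assumed) with Month 6 on target, the last borrowing day is 84 or 77. All shares are of calendar days, not of patients.

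**Step 3: prior-visit sensitivity analysis.** For a switch before the Month 3 visit with no unscheduled visit in between, the prior visit is Visit 1. Its satisfaction value is used directly, with nothing missing.

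**Step 4: possible size in the primary model.** The documents give no missingness rates, so this is illustration only. Assume 1500 patients, 8% escalating per interval, no true effect of satisfaction, mean scores of 1.6 (prior drug) and 2.6 (tofacitinib), SD 1, and Month 3 satisfaction missing in 10% of non-escalators. The model is logistic by visit, as a stand-in for the planned recurrent-event Cox model, without the other factors or confounders.

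| Missing in escalators | All-visit odds ratio per point, every missing case borrowing Visit 1 | False-positive rate, every missing case borrowing | False-positive rate, about two thirds borrowing |
|---|---|---|---|
| 20% | about 0.99 | 5 to 9% | about 7% |
| 60% | about 0.94 | 39 to 48% | 17 to 18% |

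At 40% missing the odds ratio was about 0.97. Ranges span repeated runs with simulation error of a few points. The two-thirds column assumes escalation days uniform over Days 2 to 136. With equal missingness there is essentially no bias.

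**The case against.** **Borrowing is conditional.** In the main FAS model it needs Month 3 satisfaction to be missing and no nearer unscheduled rating. SAP 9.2.6 marks all PPAS models and the FAS model with continuous DAS28 as using no imputation. This stands and limits the reach of the imputation route. It does not touch the shift table. Nor does it touch the prior-visit models, where Visit 1 enters as an observed value.

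**The covariate is not tofacitinib satisfaction by name.** This is correct: SAP 7.3.1(f) covers treatment in general, since patients are followed after switching. At a first early escalation, however, the treatment in use is tofacitinib, alone or in combination, and the prior-drug score does not describe it.

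**The SAP already restricts the display.** Endpoint (k) is satisfaction over time, and SAP 7.1.2.11 defines no change score. Since Visit 1 has no preceding visit, the by-visit table in effect starts at Month 3. This largely stands for that table. The shift from baseline is still called for in SAP 9.1.5 and the change in Protocol 7.9.2.2.3, and neither is labelled. A prior-drug versus tofacitinib contrast is informative once it is called that.

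**Barring Visit 1 alone would not help.** The nearest-value rule would then reach for Month 6, which for an early escalator usually rates the drug switched to, after the event. This is right, and the fix must cover it.

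**Conclusion.** The plan is wrong as written on this point. A stated rule allows a rating of different drugs to serve as one of six primary factors, and the same rating is the unlabelled baseline for a tofacitinib endpoint. The labelling problem and the prior-visit problem need no assumption about missing data. The imputation problem affects Days 2 to 91 when visits are on target and Month 3 satisfaction is missing.

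A reader might infer that the primary satisfaction result will be seriously biased, or that a large spurious hazard ratio will appear at Month 3. The documents do not support either. They give no missingness rates or escalation times, and the plan fits one model over all visits and estimates no Month 3 hazard ratio. Under the illustrative assumptions the all-visit estimate moves little. The false-positive rate rises materially only when escalators miss the Month 3 form far more often than others. The defect should be corrected because the value measures the wrong thing and the correction is cheap, not because a large bias has been shown.

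**What to change.** 1. **SAP 7.3.1(f) and 8.1.** State that satisfaction at an escalation may be filled only from a post-baseline response that rates the regimen in use before that escalation. Neither the Visit 1 value nor a rating given after the switch may be used. If no such response exists, treat satisfaction as missing and name the method, for example multiple imputation or a complete-case analysis.
2. **SAP 9.2.2, prior-visit sensitivity models (FAS and PPAS).** Exclude Visit 1 satisfaction in the same way.
3. **If Visit 1 satisfaction is wanted in the model,** enter it as a separate baseline covariate, named as satisfaction with prior treatment.
4. **SAP 9.2.3.11 and Protocol 7.9.2.2.3.** Report tofacitinib satisfaction from Month 3. Label any shift from Visit 1 as prior drug versus tofacitinib.

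The cost is SAP wording, a relabelled or altered shift table, and a matching protocol clarification. No sample-size figure changes. The downside is that some early escalators will have no usable satisfaction value; their number should be reported.

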7.5.1.4. Treatment Withdrawal

Patients experiencing adverse drug reactions as listed in the Xeljanz® SmPC or in the SmPCs of the other prescribed DMARDs with particular attention paid to Sections 4 (Contraindications), 5 (Special Warnings and 6 (Precautions)] should be monitored and if indicated, treatment should be withdrawn according to provision of the respective SmPC. If treatment with Tofacitinib or other DMARDs is withdrawn patients are followed up until the end of the observation period unless they withdraw from the study (see section 8.2).

7.5.2. Schedule of Activities

The schedule of activities table provides an overview of the visits that may be documented. Refer to the STUDY PROCEDURES and ASSESSMENTS sections of the protocol for detailed information on each documentation and assessment.

According to his clinical practice the HCP may schedule visits (unplanned visits) in addition to those listed on the schedule of activities, in order to conduct evaluations or assessments required to protect the well-being of the patient. As this is a non-interventional study none of these visits are mandatory and every visit should be scheduled according to clinical practice.

Table 7. Schedule of Activities

Study Week	Baseline (Enrolment)	Month 3	Month 6	Month 9	Month 12	Month 15	Month 18	Month 21	Month 24
Visit Number	1	2	3	4	5	6	7	8	9
Informed Consent	x								
Initial diagnosis of RA	x								
Prognostic factors	x								
Relevant comorbidities	x								
Demographic data	x								
Insurance type	x								
Smoking history and current smoking status	x								
Physical Examination (weight, height)	x								
Inclusion/Exclusion criteria	x								
Varicella vaccination status	x								
Prior drug treatment of RA	x								
RA-treatment with Tofacitinib and/or other DMARDs	x	x	x	x	x	x	x	x	x
Concomitant treatment of RA with Glucocorticoids	x	x	x	x	x	x	x	x	x

Tofacitinib citrate

A3921302 OBSERVATIONAL PLAN NON-INTERVENTIONAL STUDY

Final, 23 August 2017

Inflammatory Markers	x	x	x	x	x	x	x	x	x
Documentation of AE	x	x	x	x	x	x	x	x	x
Number of swollen and tender joints	x	x	x	x	x	x	x	x	x
Duration of Morning stiffness	x	x	x	x	x	x	x	x	x
Patient's Global Assessment of Arthritis	x	x	x	x	x	x	x	x	x
Physician's Global Assessment of Arthritis	x	x	x	x	x	x	x	x	x
Patient's Assessment of Arthritis Pain	x	x	x	x	x	x	x	x	x
Functional Ability Questionnaire Hannover (FFbH)	x	x	x	x	x	x	x	x	x
EuroQoL EQ-5D-3L	x	x	x	x	x	x	x	x	x
FACIT – Fatigue Scale	x	x	x	x	x	x	x	x	x
Patient's satisfaction with drug treatment	x	x	x	x	x	x	x	x	x

